## 7.2. 1 Visit 1 in Clinical Research Center (CRC) and/or Inpatient setting~8 hours

**Trial Logistics and Organizing framework:** Patients for this trial are divided into two aims. Patients enrolled for one aim, are excluded from the other aim, because the causes of the injury, which define the aim, are exclusive. Aim 1 is for post traumatic neuropathy. Aim 2 is for post surgical or post intervention neuropathy. Within each aim, there are treated patients and placebo patients. Only one patient will be evaluated at a time. Evaluation takes one day. Patients will be randomized in the Penn State University Clinical Research Center (CRC) or at the bedside, where they will stay for a period of analysis afterwards that lasts a few hours.

[figure not shown]
Eligible, consented patients will present for testing from one of three locations (emergency department, inpatient ward, or home). Patients will undergo testing in the CRC and/or bedside under the direction of trial personnel. Testing will be initiated by patients undergoing a thorough sensory and motor evaluation and establishing an intravenous line for blood sampling. A baseline blood sample and EDX study (prior to drug or placebo) and sensorimotor examination will be performed. These tests comprise part of a standardized array of tests performed hourly. This array of tests (serum 4AP level, EDX study, and sensorimotor examination) will be repeated every hour after treatment for five hours (Figure 1) during which the drug will have decreased to a level low enough to have no expected effect. The final hourly test is the return to baseline test. It is likely going to occur at the fifth hourly posttest, but is depicted separately for clarity. Only five tests after dosing will be necessary, based on our expectations from known pharmacokinetic data.

Finally, testing is concluded at the end of this period. Research subjects will be provided a diary and asked to record symptoms as instructed. The subjects will be asked to maintain the diary for 20 weeks and the diaries will be reviewed at each follow up visit and collected at or after the final 20 week visit.

[figure not shown]
**Figure 1 Legend:** Planned admission to Penn State Clinical Research Center for testing and monitoring in proposed trial design. Each patient will complete testing in one arm (either 4-AP or placebo) before discharge. Note, standard measures of nerve continuity like EDX are not usually obtained at this period of time because they typically yield no usable information. They are performed during this portion of a trial as a control on our results. Note that the return to baseline test timing is not currently known. As such, this test may not be necessary. We are currently planning on having the final hourly test be the return to baseline test. It is depicted as a separate test to note that we will ensure that the patient has returned to baseline before discharged from the CRC. Based on pharmacokinetic data, we expect that this will occur between the fourth and fifth hourly posttest.

## 7.2. 2 Follow up visits

Following the initial testing, subjects will be seen for a period of 20 weeks after injury to monitor recovery and progress. Subjects will return for follow-up visits at 2, 6, 12, 18, and 20 weeks post injury. The 2 week visit will coincide with the initial post-operative visit with the treating provider as part of standard of care. The 6, 12, and 18 week visits will be completed in the neurology clinic and EDX testing will be completed as part of standard of care (the current gold standard for continuity and recovery diagnosis). The 20 week visit will be completed in the CRC.

Subjects will receive a physical exam at all follow-up visit. EDX testing will be completed at 6, 12, and 18 week visits only. Subjects will complete a telephone interview at 9 and 15 weeks post injury at which time subjective motor and sensory function will be assessed by asking 1) Can you move your (affected extremity)? Yes or No 2) Can you feel your (affected extremity)? Yes or No. Review of the subject diary will also be completed. The 9, 15, and 20 week visits are not part of standard of care and are being done for research purposes only. Each visit or phone interview will last approximately 30 minutes. Subjects will be instructed to bring the research diary to their follow-up appointments and will be reviewed and evaluated by study personnel. At the final 20 week visit the diary will be collected. Additional follow up might be considered beyond standard of care for diary completion if required.

**Figure 2 Legend:** General timeline of trial for single patient. Note that enrolled patients are allowed to proceed with standard of care exploration of injured nerves at their own discretion (with consultation of their surgeons) all throughout this 20-week period. If the continuity or lack thereof is verified, they continue with assessments as planned. In the figure, week 1 starts after testing day (which is visit 1 in the CRC. The first follow up visit is after testing day.

### 7.3 Duration of Participation

Enrolled Subjects will be followed for a 20 week period.

### 7.4 Test Article(s) (Study Drug(s) and/or Study Device(s))

#### 7.4. 1 Description

**Generic dalfampridine (4-aminopyridine extended release formulation):** 4-AP is an organic compound with the chemical formula  $C_5H_4N-NH_2$ . The molecule is one of the three isomeric amines of pyridine. It is primarily used to manage some of the symptoms of multiple sclerosis, and is indicated for symptomatic improvement of walking in adults with several variations of the disease. 4-AP works as a potassium channel blocker. Electrophysiological studies of demyelinated axons show that augmented potassium currents increase extracellular potassium ion concentration which decreases action potential duration and amplitude which may cause conduction failure. Potassium channel blockade reverses this effect. A study has shown that 4-AP is a potent calcium channel activator and can improve synaptic and neuromuscular function by directly acting on the calcium channel beta subunit.

Subjects will receive one dose of oral dalfampridine 10 mg extended release tablets or an identical appearing placebo pill (see drug insert packet for formulation and testing information). The tablets will be over-encapsulated using Coni-Snap Empty Gelatin Capsules manufactured by Capsugel. USP grade methylcellulose will be used as filler for the active capsules and as the placebo. Placebo capsules will consist of the Con-Snap Empty Gelatin Capsule manufactured by Capsugel and the methylcellulose filler. Both pills will be formulated and tested in conformity with the FDA mandated guidelines for this trial.

#### 7.4. 2 Treatment Regimen

**Investigational Treatment – Group A and group B will both receive the same treatment with active ingredient listed below. Group A will receive the active drug and Group B will receive the placebo. This is a *single-dose study*.**

Active Ingredient: 4-aminopyridine (4-AP) 10 mg pill per dose

Inactive Ingredient: See package insert

Dosing schedule = 1 capsule.

**Other Agent(s):** Placebo

#### **7.4. 3 Method for Assigning Subject to Treatment Groups**

Subjects in both aims will be assigned to Group A or Group B using a randomization scheme. Each study participant for each aim is randomly assigned to either treatment or placebo using permuted block randomization. This randomization will be done using redcap. **This is a single-dose, pilot study.**

#### **7.4. 4 Subject Compliance Monitoring**

Not applicable. Study medication will be administered under observation.

#### **7.4. 5 Blinding of the Test Article**

Blinding will be performed by the IDS service at Penn State.

#### **7.4. 6 Receiving, Storage, Dispensing and Return**

##### **7.4 .6.1 Receipt of Test Article**

The study drug and placebo will be maintained by Penn State Investigational Drug Service (IDS). They will store, dispense and monitor all investigational supplies.

##### **7.4 .6.2 Storage**

The study drug and placebo will be maintained by Penn State Investigational Drug Service (IDS). They will store, dispense and monitor all investigational supplies. IDS will prepare and dispense study drug and placebo after randomization upon receipt of a valid prescription from the study director, which will be transported to IDS after consent.

##### **7.4 .6.3 Preparation and Dispensing**

Dalfampridine (extended release 4-aminopyridine) 10mg tablets will be obtained from Accord Pharmaceuticals by the Investigational Drug Service (IDS) Pharmacy at Penn State Health Milton S. Hershey Medical Center. IDS will then prepare blinded capsules of over-encapsulated Dalfampridine tablets and matching placebo.

##### **7.4 .6.4 Return or Destruction of the Test Article**

One 10 mg study capsule will be taken by mouth, whole in the setting of the Clinical Research Center or at the bedside. In case there is unused product if a subject chooses to withdraw after the med is dispensed, the CRC or research coordinator will return the unused product to the IDS.

Investigational product that remains at end of study will be destroyed by IDS according to Institutional policy.

##### **7.4 .6.5 Prior and Concomitant Therapy**

The study drug may not be taken together with other aminopyridine medications, including other compounded 4-AP (sometimes called 4-aminopyridine or dalfampridine).

#### **8.0 Subject Numbers and Statistical Plan**

### **8.1 Number of Subjects**

This is a pilot study. The purpose is to gain preliminary data and refine infrastructure and establish finalized routines associated with our work. We hope to recruit 50 patients to this pilot study based on our previous statistical analysis.

### **8.2 Sample size determination**

We cannot provide sample size based on the pilot nature of this study. Our purpose is to generate preliminary data that can further inform our biostatisticians. We also have found that defining our protocol procedures in the CRC will help us define statistical groups for regulatory approval of the crossover trial currently planned.

### **8.3 Statistical methods**

Consultation with the biostatistical team included separate discussions with [name] and [name]. This trial is a pilot study in preparation for an NIH funded randomized controlled trial which is currently in preparation.

Our methods will be to stratify nerve injuries based on injury severity and compare placebo to drug patients using the methods listed below:

This proposal contains two distinct aims to be investigated in two similar groups of patients.

**Aim 1:** To examine the effect of 4AP on the return of sensorimotor function and EDX sensitivity in the setting of nerve dysfunction from orthopaedic trauma. This aim tests the hypothesis that oral one-time administration of 4AP provides transient return of function and EDX sensitivity to the traumatically denervated limb in alert patients with known limb injuries not involving the central nervous system.

**Aim 2:** To examine the effect of 4AP on the return of sensorimotor function and EDX sensitivity in the setting of iatrogenic nerve injury after surgical intervention. This aim tests the identical hypothesis as in Aim 1 in a distinct group of patients, whose nerve dysfunction is the result of a clinical intervention, and whose function before that intervention was intact.

Statistical planning was performed in the design of this trial with a qualified biostatistician, who also sits on the Data Safety Monitoring Board for this study. Statistical methods will be used to evaluate both the effect of treatment as well the effects of injury type (either aim 1 or aim 2). Groups will be analyzed separately within each aim.

Categorical variables (as in the presence or absence of sensation) will be compared (between treated and untreated groups for each aim) using Chi-squared testing. Continuous data (as in nerve conduction velocity from EDX) will be compared with standard student's T testing. Grouped data variables will be first compared in linear models (accounting for mixed effects of multiple variables as indicated). Formal recommendations for the statistical methods to be used for posthoc comparisons will be made by the biostatistician designee of the DSMB ([name]), who has aided in the planning of this trial and is a non-conflicted member of the trial team.

#### **Information provided by the biostatistician collaborator:**

Data analysis for both of these aims is identical, and involves a generalized linear mixed-effects model with a logit link function (118). The separation of these aims is based on the source of the injury, the likelihood of a severed nerve (less likely in aim 2), and the patient's need for an answer to the question. In aim 1, patients may suffer additional harm to a nerve for necessary care but fundamentally, aim 1 contains patients for whom the question of nerve continuity is not the result of a surgical intervention.

Patients will undergo clinical testing for both subjective (return of feeling, motor control) and objective (withdrawal from painful stimuli, deep-tendon reflexes, sudomotor function, muscle firing) measures of function before and after administration of 4AP and placebo (all patients will receive both treatments in random order). Standard monitoring will include clinical observation for voluntary movement, electrodiagnostic testing, and serum tests to correlate circulating 4AP concentrations to diagnostic thresholds and compare those thresholds to those used for therapeutic efficacy in the current approved patient populations. The diagnostic information, in conjunction with formalized inclusion and exclusion criteria, will not affect the current standard treatment paradigm, but will inform our decisions on suspected nerve continuity and surgical exploration.

Patients with intact function prior to operative procedures often suffer trauma to a nerve iatrogenically as a result of a procedure. In these patients, the trauma is often our surgery to correct a fracture or other deformity. We will investigate the possibility of administration of oral 4AP in patients with nerve dysfunction after surgical intervention in the limb. Despite the belief that the nerve is not severed, dysfunction in these patients is indistinguishable from cases where the nerve is later discovered to be iatrogenically severed as part of the procedure. Their testing will be performed identically as in the case of aim 1, with the exception that these patients will have documented presurgical examination of the limb showing function to be intact prior to the index procedure.

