### 1.2 Primary Study Endpoints

Primary Aim and Study Endpoint: Return of voluntary function and subjective sensation not present after trauma.

**Summary of Specific Aims:** This proposal contains two distinct aims to be investigated in two similar but distinct groups of patients. This will be measured by sensory, motor and sudomotor (electrical conduction tests), and electrodiagnositc (EDX) testing.

**Aim 1:** To examine the mechanistic effect of 4AP on the return of sensorimotor function and EDX sensitivity in the setting of nerve dysfunction from orthopaedic trauma. This aim tests the hypothesis that oral one-time administration of 4AP provides transient return of function and EDX sensitivity to the traumatically denervated limb in alert patients with known limb injuries not involving the central nervous system.

**Aim 2:** To examine the mechanistic effect of 4AP on the return of sensorimotor function and EDX sensitivity in the setting of iatrogenic nerve injury after surgical intervention. This aim tests the identical hypothesis as in Aim 1 in a distinct group of patients, whose nerve dysfunction is the result of a clinical intervention, and whose function before that intervention was intact.

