#### **3.3. 2 Follow-up for withdrawn subjects**

In order to maintain a sample size of 25-34 subjects per aim (note that there are two aim target groups), those withdrawn from the study will be replaced. Subjects withdrawn for safety reasons will be followed up by regular checking up with them over the phone (and or other tests if necessary).

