Research study participant randomization for this trial is segregated by aim. Aim 1 research study participants are randomized to treatment or placebo separately from aim 2 research study participants. Each study participant for each aim is randomly assigned to either treatment or placebo using permuted block randomization.

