## **11.0 Potential Benefits to Subjects and Others**

### **11.1 Potential Benefits to Subjects**

A known risk in nerve injury is a delay in recovery of function attributable to inability to correctly diagnose a nerve laceration without EDX, which only becomes sensitive to the continuity of the nerve weeks after the injury. It is well known that early surgical exploration and repair of lacerations of the nerve is best in patients with known nerve lacerations and detrimental for patients found at surgery to have an unsevered nerve. As this trial offers no change in the overall standard of care for nerve patients other than a trial of a drug to see if it returns function or sensation (clear indications that the nerve is not severed), this trial does not alter the standard of care for these patients. The benefits are a clear indication of the status of the nerve weeks before the gold standard test can reveal the same information – but this benefit is only realized in the drug group and only if return of function is demonstrated. 4-AP is a known neuro-enhancing agent we hypothesize will potentially return function transiently but long enough to reveal those patients whose nerves are intact but not working. Furthermore, we predict this diagnostic intervention will also limit the difficulty and stigma associated with not knowing if their nerve has been cut, again a direct benefit only realized when continuity is demonstrated. This trial only affects patient decisions to pursue further treatment if return of function is clearly demonstrated. Otherwise, patients might have no return of function either because their nerve was indeed severed in the trauma or if they received placebo. As such, no direct conclusions or alterations in patient care will be based on these results for trial patients. Also, since there are additional research visits included at two week intervals in this trial, recovery will be followed with greater accuracy over time.

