**Patient Source:** Patients will come from two sources. The first will be traumatized patients presenting with nerve dysfunction. These patients often have concomitant orthopaedic injuries, which require stabilization. If the nerve was dysfunctional before intervention, then the patient will be included as a recruit for aim 1. The second source is patients who suffer nerve dysfunction after a surgery or intervention where nerve injury may not have been expected, as is the case with routine fracture fixation or joint arthroplasty procedures. In such cases, post-intervention examination may reveal a loss of nerve function where the continuity of the nerve again cannot be established. These patients, owing to their intact nerve function before the intervention, will be included as recruits to aim 2. In point of fact, both groups of patients have the same phenotypic condition, namely the loss of nerve function where the continuity of the nerve is not demonstrable. However, they are grouped into differing aims because the latter group suffers nerve dysfunction as the result of an intervention or surgical procedure and critically, these patients will have a clear pre-intervention examination without any nerve dysfunction.

Splitting aims is necessary because of the differing means by which the patient is injured and the different circumstances of injury. Surgeons will often tell patients who would qualify for aim 2 that they are absolutely sure that the nerve is not severed, altering the pre-test/pre-trial likelihood that the patient may feel a return of function even if exposed to the placebo. We therefore intend to keep the recruitment and counselling of aim 2 patients separate from those who present after traumatic, non-iatrogenic nerve injury.

**Patient Selection and Availability Patient Availability and Cohort Query Analytics:** Ambiguous nerve continuity is common in our medical center. Initial estimates, based on stakeholder provider interviews,

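### If no placebo patient shows return of function, the logit mixed model gives no finite effect estimate, and section 8.3 does not say whether that model or the chi-squared test decides.

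*Combined protocol and SAP*

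**What the plan says.** Section 8.3 names two methods for a binary outcome. Its main text assigns presence-or-absence variables, treated against untreated within each aim, to a chi-squared test. The biostatistician's text that follows says: "Data analysis for both of these aims is identical, and involves a generalized linear mixed-effects model with a logit link function". Neither is called primary. The model has no stated random-effects structure, estimation method, test or handling of empty cells.

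The primary endpoint (section 1.2) is: "Return of voluntary function and subjective sensation not present after trauma". It is absent at baseline by definition. Section 7.2.1 has five hourly post-dose assessments on the trial day and section 7.2.2 follows recovery to 20 weeks; no time point is fixed for the endpoint.

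On numbers, section 3.3.2 says "In order to maintain a sample size of 25-34 subjects per aim" and section 8.1 says "We hope to recruit 50 patients to this pilot study". Patients are "randomly assigned to either treatment or placebo using permuted block randomization" separately in each aim, with no ratio given, and section 8.3 analyses the aims separately.

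On placebo response the text points two ways. Section 11.1 says "this benefit is only realized in the drug group and only if return of function is demonstrated" and that "patients might have no return of function either because their nerve was indeed severed in the trauma or if they received placebo". Section 15.2 says that surgeons' reassurance of aim 2 patients has the effect of "altering the pre-test/pre-trial likelihood that the patient may feel a return of function even if exposed to the placebo".

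**The concern.** A logit model estimates a log odds ratio. When one arm has no events, the odds in that arm are estimated as zero and the log odds ratio has no finite maximum-likelihood value. A random patient effect does not change this.

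The outcome that the hypothesis describes, function returning briefly on drug and not on placebo, is where this is most likely. Two things are at stake. First, section 8.2 says that the pilot exists to give preliminary data to the biostatisticians, and in this outcome the named model would give them no odds ratio and no interval. Second, a Wald test from that model and the chi-squared test could give opposite answers on the same data. With no ranking in the plan, the choice between them could be made after the results are seen.

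**Working it through.** **Inputs.** The documents state no alpha, power, effect size or response rate, so there is no figure to reproduce. The counts agree: 2 × 25 = 50, and the interim look at 13 patients per aim (section 19.1.2) is about half of 25. Assumed here: 1:1 allocation, so 25 per aim gives 12 v 13 and 34 gives 17 v 17; two-sided 5%; a binary patient-level outcome; drug responders positive at 2 to 4 of the five hours.

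**Step 1: why the estimate is infinite.** Let b0 be the placebo log odds, b1 the treatment effect and s the random-intercept SD. A placebo patient with five negative hours contributes the average over the random effect of the product of five terms 1 − expit(b0 + s·u). For any s this rises towards 1 as b0 falls. The drug arm depends only on b0 + b1 and s. Lowering b0 and raising b1 by the same amount therefore never lowers the likelihood, and b1 has no finite maximum.

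**Step 2: numerical check.**
- 0/12 v 7/13, random-intercept logit: the profile log-likelihood is −35.950 at every b1 tried from 20 to 40. With b1 = 0 it is −42.837. The likelihood-ratio statistic is 2 × (42.837 − 35.950) = 13.77, p = 0.0002.
- 0/12 v 8/13, same model in a standard mixed-model package: b1 = 22.7, SE = 17,259, Wald p = 0.999, with convergence warnings. The likelihood-ratio p is 0.00004.
- Chi-squared for 0/12 v 7/13: 25 × (7 × 12 − 6 × 0)² / (13 × 12 × 7 × 18) = 8.97, p = 0.003. Fisher p = 0.005.
- One placebo responder removes the problem. For 1/12 v 7/13 in a plain logit, the log odds ratio is ln[(7/6)/(1/11)] = 2.55, SE = √(1/7 + 1/6 + 1/1 + 1/11) = 1.18, Wald p = 0.03.

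**Step 3: how likely it is.** P(no placebo responder) = (1 − p)^n:

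| True placebo rate | n = 12 | n = 17 |
|---|---|---|
| 2% | 78% | 71% |
| 5% | 54% | 42% |
| 10% | 28% | 17% |
| 20% | 7% | 2% |

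At the interim look, with about 6 placebo patients per aim, it is 0.95^6 = 74% at 5% and 0.90^6 = 53% at 10%.

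**Step 4: what the choice of test costs.** Exact enumeration over all 12 v 13 tables, with a true drug response of 50%. Wald is from a plain patient-level logit, counting separated tables as non-significant. The range for the exact unconditional (Boschloo) test reflects different two-sided definitions.

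| Placebo rate | Wald | Chi-squared | Boschloo |
|---|---|---|---|
| 2% | 10% | 89% | 82–89% |
| 5% | 20% | 79% | 74–79% |
| 10% | 27% | 62% | 59–62% |

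Separation is not the whole gap. At 10% the gap is 62 − 27 = 35 points, while separation occurs in 28% of trials. The rest is the Wald test's weakness in small samples.

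**The case against.** Four points weigh against a stronger statement.

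- A reader might infer that the named model would declare a large drug effect non-significant. The documents do not support that, because they name a model and no test. Wald is a software habit, and the likelihood-ratio test from the same model gives p = 0.0002 in the example. This stands for the p-value. It does not supply an estimate: the odds ratio remains infinite.
- A reader might infer that the plan has no working test. It has one: the chi-squared test of section 8.3 has about the same power as the exact unconditional test. This also stands. What is missing is a ranking of the two methods.
- A reader might infer that the protocol expects no return at all on placebo. Section 11.1 leans that way, but no section states a zero rate and section 15.2 anticipates some felt return on placebo in aim 2. Several modalities tested at five hours give many chances for one positive record, and one responder restores a finite estimate. By week 20 nerves in continuity may recover in either arm. The problem therefore belongs mainly to the trial day, aim 1 and the objective measures.
- The model text may have been written for another design. It says that every patient receives both treatments, against the parallel groups of sections 7.1 and 7.2, and it cites reference 118 when the list ends at 39. That conflict needs correcting, but a crossover would not cure separation: with no positive placebo period the estimate is still infinite.

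It would also be wrong to say that a stronger drug makes detection less likely. Separation of this kind depends on the placebo rate.

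**Conclusion.** The concern holds in limited form, at moderate severity. If no placebo patient in an aim shows return, the model named for both aims gives no finite effect size or interval, and a Wald test from it is uninformative. At 12 per arm the chance of this runs from 78% at a 2% placebo rate to 7% at 20%; at 17 per arm, from 71% to 2%. The true rate is unknown, so the range is the finding.

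The plan is not shown to be unable to detect a drug effect. The defect is that it names two methods that could contradict each other (p = 0.003 by chi-squared, Wald p near 1 for 0/12 v 7/13), ranks neither, and has no rule for an empty cell. The figures rest on 1:1 allocation, a binary trial-day outcome, two-sided 5% and, for power, a 50% drug response. None of these is stated in the documents.

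**What to change.** In section 8.3:

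- Make one patient-level binary comparison within each aim the main analysis, at a stated trial-day definition of return. Use an exact unconditional test (such as Boschloo, with its two-sided definition stated) or a re-randomisation test that follows the permuted blocks.
- Report the risk difference with an exact or score confidence interval. It stays finite with an empty cell and is what the next trial needs.
- Keep the logit mixed model as supportive. State its random effects, fit it by penalised likelihood (Firth-type or a weakly informative prior), and test it by likelihood ratio or permutation and not by Wald. Permutation avoids relying on large-sample theory with 12 to 17 per arm.
- State where the chi-squared test stands relative to these, apply the same main test at the interim look, and align the model text with the parallel-group design.

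The cost is SAP wording and a few lines of code, with no new data. It should be settled before unblinding and before the first interim analysis.
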